8 ASSESSMENT OF SAFETY

8.1 INVESTIGATOR RESPONSIBILITIES

The Investigator is responsible for monitoring the safety of patients who have enrolled in the study and for accurately documenting and reporting information as described in the following sections.

8.2 MEDICAL COVER

The Principal Investigator (PI) is responsible for ensuring patients have access to 24 hour advice and/or care. Patients will be provided with the necessary contact numbers for both normal working and out of hours care. A copy of the protocol must be made available out of hours to ward staff and clinicians on call so that the appropriate advice may be given to the patient, the patient's relative or other care giver (for example General Practitioner (GP)). The CI/PI must ensure that should the on call clinician or ward staff require more advice than is in this protocol, that they have access to the Investigator or delegated members of the clinical team who can answer any questions.

8.3 ADVERSE EVENT DEFINITIONS

8.3.1 Adverse event (AE)

An AE is any untoward, undesired or unplanned occurrence in a patient administered an IMP, a comparator product or an approved drug. An AE can be a sign, symptom, disease, and/or laboratory or physiological observation that may or may not be related to the IMP or comparator.

An AE includes but is not limited to those in the following list.

- A clinically significant worsening of a pre-existing condition. This includes conditions that may resolve completely and then become abnormal again.
- AEs occurring from an overdose of an IMP, whether accidental or intentional.
- AEs occurring from lack of efficacy of an IMP, for example, if the Investigator suspects that a drug batch is not efficacious.

Other reportable events that must be treated as AEs are listed below.

- Pregnancy exposure to the IMP. Any pregnancy occurring in a patient or a patient's partner during exposure to an IMP or occurring within 7 days of the last IMP administration, must be reported to the Pharmacovigilance Department in the same timelines as an SAE. These should be reported even if the patient is withdrawn from the study.
- Overdose with or without an AE.
- Inadvertent or accidental exposure to an IMP with or without an AE, including for example, spillage of the IMP that contaminates staff.
- Any AE that could be related to the protocol procedures, and which could modify the conduct of the study.

8.3.2 Serious adverse event (SAE)

An SAE is any AE, regardless of dose, causality or expectedness, that:

- results in death;

CONFIDENTIAL

- is life-threatening*;
- requires in-patient hospitalisation or prolongs existing in-patient hospitalisation (some hospitalisations are exempt from SAE reporting – see Section 8.4);
- results in persistent or significant incapacity or disability;
- is a congenital anomaly or birth defect;
- is any other medically important event.**

* A life-threatening event is defined as an event when the patient was at substantial risk of dying at the time of the adverse event, or use or continued use of the device or other medical product might have resulted in the death of the patient.

** A medically important event is defined as any event that may jeopardise the patient or may require intervention to prevent one of the outcomes listed above. Examples include allergic bronchospasm (a serious problem with breathing) requiring treatment in an emergency room, serious blood dyscrasias (blood disorders) or seizures/convulsions that do not result in hospitalization. The development of drug dependence or drug abuse would also be examples of important medical events.

For fatal SAEs, wherever possible report the cause of death as an SAE with a fatal outcome rather than reporting death as the SAE term. When available the autopsy report will be provided to the Sponsor.

If during the course of the study, other medically important events are identified and there is a requirement to report specific events outside of the standard criteria, this will be communicated to site and the protocol will be updated to reflect this.

8.3.3 Determining AE causality

The relationship of an AE to the IMP is determined as follows.

Highly probable 
• Starts within a time related to the IMP administration and• No obvious alternative medical explanation.
Probable 
• Starts within a time related to the IMP administration and• Cannot be reasonably explained by known characteristics of the patient's clinical state.
Possible 
• Starts within a time related to the IMP administration and• A causal relationship between the IMP and the AE is at least a reasonable possibility.
Unlikely 
• The time association or the patient's clinical state is such that the study drug is not likely to have had an association with the observed effect.
Not related

- The AE is definitely not associated with the IMP administered.

Note: Drug-related refers to events assessed as possible, probable or highly probable.

The Investigator must endeavour to obtain sufficient information to determine the causality of the AE (i.e. IMP(s), other illness, progressive malignancy etc) and must provide his/her opinion of the causal relationship between each AE and each IMP(s). This may require instituting supplementary investigations of significant AEs based on their clinical judgement of the likely causative factors and/or include seeking a further opinion from a specialist in the field of the AE.

8.3.4 Expectedness

Assessment of expectedness will be made by the Pharmacovigilance Department against the current version of the Investigator Brochure for [¹²⁴I]mIBG and the current SmPC for [¹²³I]mIBG.

8.3.5 Suspected, unexpected, serious, adverse reactions (SUSARs)

A SUSAR is a suspected, unexpected, serious adverse reaction. All AEs and SAEs will be assessed by CDD for seriousness, causality and expectedness. The Pharmacovigilance Department will expedite all SUSARs to the relevant Competent Authority/Authorities and the relevant Research Ethics Committee (REC) within the timelines specified in legislation (SI 2004/1031 as amended).

8.4 COLLECTION OF SAFETY INFORMATION

8.4.1 Screening failures

For patients who fail screening, SAEs must be reported to the Pharmacovigilance Department, CDD from the date of consent until the date the patient is confirmed as ineligible.

8.4.2 Eligible patients

For eligible patients, SAE and AE collection and monitoring will commence at the time the patient gives their written consent to participate in the trial by signing the main study consent form and will continue until 7 days after the last administration of IMP or until the patient starts another anti-cancer therapy.

Should an Investigator become aware of any drug-related SAEs after this 7 day period, these must also be reported to the CDD within the expedited timelines in Section 9.4.

8.4.3 Follow-up of AEs and SAEs

Follow-up of AEs with a causality of possible, probable or highly probable will continue until the events resolve, stabilise or the patient starts another anti-cancer therapy.

The Pharmacovigilance Department will make requests for further information on SAEs to the trial site at regular intervals. Requested follow-up information should be reported to the Pharmacovigilance Department in a timely manner and as soon as possible after receipt of the follow-up request. For fatal or life-threatening cases, follow-up information must be reported to the Pharmacovigilance Department as soon as possible.

8.4.4 Other safety information of interest

We will also collect information on the following situations, whether they are associated with an AE or not:

- Overdose (*any dose above that specified in the protocol, not necessarily intentional*)

CONFIDENTIAL

- Abuse or misuse
- Medication error (*any unintentional error in the dispensing or administration of an IMP*)
- Occupational exposure (*to a person other than the patient, for example spilling of IMP on hands of nurse or splashing in the eye*)

Any occurrences of these should be reported in the same manner as SAEs (Section 9.4).

8.5 EXPEDITED REPORTING OF SAEs TO PHARMACOVIGILANCE

All SAEs, regardless of causality, must be reported to the Pharmacovigilance Department in an expedited manner.

SAEs should be documented on an SAE report form, using the completion guidelines provided.

The SAE report form should be emailed to Pharmacovigilance Department within 24 hours of site staff becoming aware of the SAE.

Email: [contact]

Each episode of an SAE must be recorded on a separate SAE report form. The NCI CTCAE Version 4.02 must be used to grade each SAE, and the worst grade recorded. If new or amended information on a previously reported SAE becomes available, the Investigator should report this to the Pharmacovigilance Department on a new SAE report form.

If the SAE has not been reported within the specified timeframes, a reason for lateness must be added on the email cover sheet when sending the SAE report form to the Pharmacovigilance Department.

Should the Investigator become aware of any drug-related SAEs after the patient goes 'off study', these must also be reported to the Pharmacovigilance Department within the specified timelines above.

8.5.1 Events exempt from reporting as SAEs to Pharmacovigilance

Events specified in this section do not require reporting as SAEs in this study, unless hospitalisation is prolonged for any reason and then an SAE form must be completed. The events must still be recorded in the appropriate section of the eCRF.

Elective admissions – Elective admissions to hospital for procedures which were planned prior to entering the trial are not SAEs. Hospitalisation for administration of an IMP and conduct of scans according to the study protocol is also exempt from being reported as an SAE.

8.6 RECORDING OF AEs AND SAEs IN eCRFs

All AEs, including SAEs, must be recorded in the eCRF for eligible patients. All concomitant medications, including herbal medications and supplements must be recorded. Any therapy used to treat the event must be recorded. The eCRF will be reconciled with the safety database during and at the end of the study. Therefore, the sites should ensure the data entered on the SAE report form and the data entered into the eCRF are consistent. The CDD Medical Advisor and the Investigator(s) will regularly review the safety data from both the safety and the clinical database.

8.7 FOLLOW-UP OF AEs AND SAEs

Follow-up will continue until all the necessary safety data for the event has been gathered and until resolution, recovery to baseline, or stabilisation of these events, unless the patients starts another

CONFIDENTIAL

anti-cancer therapy. The Pharmacovigilance Department will make requests for further information to the study site at regular intervals. Requested follow-up information should be reported to the Pharmacovigilance Department in a timely manner and as soon as possible after receipt of the follow-up request. For fatal or life-threatening cases, follow-up information should be reported to the Pharmacovigilance Department as soon as possible.

8.8 URGENT SAFETY MEASURES

The Sponsor or Investigator may take appropriate urgent safety measures (USMs) in order to protect the patient of a clinical study against any immediate hazard to their health or safety. This includes procedures taken to protect patients from pandemics or infections that pose serious risk to human health.

USMs may be taken without prior authorisation from the competent authority.

The Medicines and Healthcare products Regulations Agency (MHRA) and the REC must be notified within three days of such measures being taken.

Should the site initiate a USM, the Investigator must inform the Sponsor immediately either by:

- email: [contact]; or
- [contact];

The notification must include:

- the date of the USM;
- who took the decision; and
- why action was taken.

The Sponsor will then notify the MHRA and the REC within three days of USM initiation.

8.9 PREGNANCY

Female patients who become pregnant from the time of informed consent being signed to off-study, must be withdrawn from study treatment immediately.

The Investigator must make every effort to try and ensure that a clinical trial patient or a partner of a clinical trial patient does not become pregnant during the trial or for seven days afterwards. This should be done as part of the consent process by explaining clearly to the patient the potential dangers of becoming pregnant and also providing each patient with information about appropriate medically approved contraception. Two forms of medically approved contraception should be used, such as:

- oral contraceptives and condom;
- intra-uterine device (IUD) and condom;
- diaphragms with spermicidal gel and condom.
- Contraception should be effective before the patient is enrolled on the trial, throughout the trial and for six months after the administration of [¹²⁴I]mIBG.

CONFIDENTIAL

- It should be explained to the patient that if his partner is pregnant or breast-feeding when he is enrolled on the trial, the patient should use barrier method contraception (condom plus spermicidal gel) to prevent the unborn baby or the baby being exposed to the [¹²⁴I]mIBG.
- However, if a patient or a partner of a patient does become pregnant, the reporting procedures below must be followed.

Any pregnancy occurring in a patient or a patient's partner occurring within seven days of administration of either [¹²³I]mIBG or [¹²⁴I]mIBG must be reported to the Pharmacovigilance Department within 24 hours of the site staff becoming aware of it using a Pregnancy Report Form (provided in the ITF). It is the Investigator's responsibility to obtain consent for follow-up from the patient or patient's partner. In addition, the Investigator must be made aware of the need to obtain contact details for the patient's partner's General Practitioner. The Pharmacovigilance Department will follow-up all pregnancies for the pregnancy outcome via the Investigator, using a Pregnancy Report Form.

The Investigator must ensure that all patients are aware at the start of a clinical trial of the importance of reporting all pregnancies (in themselves and their partners) that occur whilst being treated with the IMP and occurring up to seven days after the last [¹²⁴I]mIBG administration. The Investigator should offer counselling to the patient and/or the partner, and discuss the risks of continuing with the pregnancy and the possible effects on the foetus. Monitoring of the patient should continue until the conclusion of the pregnancy, if the patient or patient's partner has consented to this. Monitoring of the baby should continue until 12 months after birth, if the patient or patient's partner has consented to this.

9 ASSESSMENT OF IMAGING TECHNIQUES

9.1 PRIMARY ANALYSIS

Analysis of [¹²⁴I]mIBG PET/CT and [¹²³I]mIBG planar scintigraphy will be performed retrospectively by an agreed number of observers who are experienced in the assessment of neuroblastoma. The observers will perform the analysis separately from each other and will be blinded from the scores of the other observers. An observer will perform their review of each modality for a patient several weeks apart. [¹²³I]mIBG imaging and [¹²⁴I]mIBG PET/CT imaging will be reviewed on a Hermes workstation (Hermes Medical Solutions, Sweden). Observers may perform their assessment of study imaging data in batches throughout the study but will not share their scores until the conditions are met to trigger the interim and final analyses as described in section 12.2.

For each modality, suspected lesions will be judged positive, negative, or equivocal with regard to neuroblastoma involvement by each observer. A final determination of each lesion as positive, negative or equivocal will be established through consensus between all observers:

- Positive – all reviewers consider it positive
- Negative – all reviewers consider it negative
- Equivocal – fewer than all reviewers can agree on whether the lesion is positive or negative

The scores for each modality will be submitted to the statistician at the interim and final analyses to meet the primary endpoint. The percentage of positive findings identified on routine [¹²³I]mIBG planar scintigraphy also identified by the novel [¹²⁴I]mIBG PET/CT will be determined. Recruitment will cease during the interim analysis.

9.2 SECONDARY ANALYSIS

The agreed number of experienced observers will perform the same analysis of [¹²³I]mIBG scintigraphy by 3D SPECT where this was performed as part of the routine imaging for a patient. Using the method described in Section 9.1 the observers will score suspected lesions for this modality. The percentage of positive findings identified on routine [¹²³I]mIBG scintigraphy by 3D SPECT also identified by the novel [¹²⁴I]mIBG PET/CT will be determined.

9.3 TERTIARY ANALYSES

[REDACTED]

[REDACTED]

[REDACTED]

[REDACTED]

[REDACTED]

[REDACTED]

10 PATIENT WITHDRAWAL BEFORE COMPLETION OF IMAGING SCHEDULE

The Investigator must make every reasonable effort to keep each patient on study for the whole duration of the study (i.e. until the Off-Study assessment has been completed). However, if the Investigator removes a patient from the study or if the patient declines further participation, the 'off-study' assessments should ideally be performed before any subsequent therapeutic intervention. All the results of the evaluations and observations, together with a description of the reasons for withdrawal from the study, must be recorded in the medical records and in the eCRF.

Patients who are removed from the study due to AEs (clinical or laboratory) will be treated and followed according to accepted medical practice. All pertinent information concerning the outcome of such treatment must be recorded in the eCRF and on the SAE report form where necessary.

The following are justifiable reasons for the Investigator to withdraw a patient from the study.

- AE/SAE
- Withdrawal of consent or assent by a parent/guardian or by the patient as applicable
- Serious violation of the study protocol
- Sponsor's decision to terminate the study
- Failure to meet the Clinical Criteria for [¹²⁴I]mIBG imaging (section 4.1.3)
- Withdrawal by the Investigator for clinical reasons not related to the study imaging (including pregnancy)

11 DEFINING THE END OF TRIAL

The 'end of trial' will be declared when one of the following is fulfilled:

- [¹²⁴I]mIBG Solution for Injection is considered too toxic to scan any further patients before the required number of patients have been recruited.
- Following the interim analysis, it is confirmed the trial is to stop due to futility as per Section 12.1 (end of trial will be the date of this decision).
- Following the interim analysis, it is confirmed the trial is to stop due to efficacy as per Section 12.1 (end of trial will be the date of this decision).
- If recruitment continues as allowed under the protocol beyond the interim analysis. Last Patient Last Visit is defined as the date when the last patient completes their participation in the trial, which will be either completion of the Off-study assessment or early withdrawal from the trial.

It is the responsibility of the CDD to notify the MHRA and the REC of the 'end of the trial'.

In cases of early termination of the study (for example, due to toxicity) or a temporary halt by the CDD, the CDD will notify the MHRA and the REC within 15 days of the decision and a detailed, written explanation for the termination/halt will be given. The entire study will be terminated when:

- [¹²⁴I]mIBG Solution for Injection is considered too toxic to scan any further patients before the required number of patients have been recruited.
- The stated minimum number of evaluable patients has been reached.
- The stated objectives of the study are achieved.

Regardless of the reason for termination, all data available for patients at the time of termination of the study must be recorded in the eCRF.

12 DATA ANALYSIS AND STATISTICAL CONSIDERATIONS

12.1 SAMPLE SIZE

The primary endpoint of the study is the percentage of lesions identified as positive using [¹²³I]mIBG planar scintigraphy which are also identified as positive on [¹²⁴I]mIBG PET/CT. The definition of a positive lesion is described in section 9.1. The aim is to prove that there is more than 90% agreement between the methods, with an expected level of agreement of 97%. Patients are expected to have a median of 3 lesions. Lesions are assumed to be independent within patients for the primary analysis. The following two stage design will be used, where the true proportion of agreement is denoted by P:

In the first stage, a total of at least 9 patients will be recruited, with a combined total of at least 50 lesions positive on [¹²³I]mIBG. Initially an exact one-sided binomial test of the null hypothesis: $P \geq 97\%$ will be done using $\alpha = 0.05$. If this is rejected in favour of the alternative hypothesis $P < 97\%$, the trial will be stopped early for futility. With a total of exactly 50 lesions this will occur if 45 or fewer lesions are also positive on [¹²⁴I]mIBG PET/CT.

If the null hypothesis is accepted, a further one-sided binomial test of the null hypothesis: $P \leq 90\%$ will be done using $\alpha = 0.025$. If this is rejected in favour of the alternative hypothesis $P > 90\%$ then the trial may be stopped early for efficacy. With a total of 50 lesions this will occur only if all 50 lesions are also positive in [¹²⁴I]mIBG PET/CT. If this null hypothesis is not rejected, the trial will continue to the second and final stage.

The second stage will end when an overall total of at least 33 patients with at least 100 lesions have been recruited. An exact one-sided binomial test of the null hypothesis: $P \leq 90\%$ will be done using $\alpha = 0.025$. If this is rejected in favour of the alternative hypothesis $P > 90\%$ then the trial will be declared a success. With a total of 100 lesions this will occur if at least 96 lesions are also positive on [¹²⁴I]mIBG PET/CT.

Overall this design has 82% power and an alpha of 0.03. If the true percentage of agreement is 97% then there is a 22% chance of stopping early for efficacy, and if the true percentage of agreement of 90% then there is a 57% chance of stopping early for futility. The total sample size of 100 lesions was calculated based on a single stage A'hern design with $p_0 = 0.9$ and $p_1 = 0.97$, and the overall power and alpha has been calculated based on exact binomial probabilities.

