12.2 INTERIM AND FINAL ANALYSIS

The interim analysis will be conducted once both of the following conditions are met:

- At least 50 lesions have been identified on [¹²³I]mIBG planar scintigraphy. These lesions will have been identified as positive by a Nuclear Medicine physician at the investigational site.
- A minimum of 9 evaluable patients have completed the study.

The analysis will be done using all identified lesions from at least 9 patients. Therefore, the total number of lesions is expected to be more than 50. The number of lesions identified on [¹²³I]mIBG planar scintigraphy will be reported to the CSM at the CDD at the time of sponsor authorisation of the supply of the [¹²⁴I]mIBG tracer from the manufacturing organisation to the investigational site. The CSM will communicate to the observers and the statistician when the conditions have been met to trigger the interim analysis.

The interim analysis will assess the primary endpoint by comparison of the number of positive lesions detected on [¹²³I]mIBG planar scintigraphy and [¹²⁴I]mIBG PET/CT in order to compare the two modalities. The imaging data will be analysed and scored separately by an agreed number of observers using the same scoring method as described in Section 9.1 in order to prevent subjective bias. Observers may perform their assessment of study imaging data prior to the interim and final

analyses in batches but will remain blinded to the scores of the other observers until the interim and final analyses are triggered and they meet to perform the consensus reviews. Assessment of the reported safety data will be performed at the interim review and will be considered as part of the decision whether to continue recruitment. The feasibility of recruitment of the required minimum number of patients will also be considered in this decision.

The final analysis will be conducted after one of the following conditions is met:

- The study is terminated early
- The end of trial as defined in Section 11 has been reached.

Following lesion detection the agreed number of experienced observers will also perform a semi-quantitative assessment of [¹²⁴I]mIBG PET/CT scans and [¹²³I]mIBG imaging employing SUVmean and SUVmax. The level of disease involvement will be assessed using the International Society of Paediatric Oncology Europe Neuroblastoma (SIOPEN) scoring method and the Curie scoring method (see Appendix 5).

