The overall study design including the second stage has 82 % power and an α of 0.03. If the true percentage of agreement is 97 % then there is a 22 % chance of stopping early for efficacy; if the true percentage of agreement of 90% then there is a 57 % chance of stopping early for futility. The total sample size of 100 lesions was calculated based on a single stage A'hern design with $p_0 = 0.90$ and $p_1 = 0.97$, and the overall power and α has been calculated based on exact binomial probabilities.

2 Analysis Sets

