2.1 Definition of Analysis Sets

The following trial populations have been defined for reporting purposes:

- Full Analysis Population: All patients enrolled to the study.
- Safety [^{123}I]mIBG Population: All patients who receive [^{123}I]mIBG (these patients may or may not have received [^{124}I]mIBG).
- Safety [^{123}I]mIBG and [^{124}I]mIBG Population: All patients who receive both [^{123}I]mIBG and [^{124}I]mIBG.
- Evaluable Population: Patients who received both [^{123}I]mIBG and [^{124}I]mIBG and underwent trial scanning with both agents. All lesions from these patients are considered independent of one another.
- [REDACTED]
- A sensitivity analysis will be informed in those in the evaluable population and have less than 10 lesions.

The primary analysis set will consist of all patients consented to the study, with at least one positive lesion recorded on routine [^{123}I]mIBG planar scintigraphy, who have also completed [^{124}I]mIBG PET/CT within 3 to 21 days as planned i.e. the Evaluable Population. Patients who did not undergo both [^{123}I]mIBG planar scintigraphy and [^{124}I]mIBG PET/CT will be excluded from this set, as will any patient where zero positive lesions were found on [^{123}I]mIBG planar scintigraphy, and patients with more than 21 days between [^{123}I]mIBG and [^{124}I]mIBG scans.

The safety analysis set for the secondary objective will consist of all patients consented to the study who received any dose of [^{124}I]mIBG at any time whether or not they subsequently completed any of the planned imaging procedures i.e. the Safety [^{123}I]mIBG and [^{124}I]mIBG Population. Additionally, all AEs occurring post consent and prior to [^{124}I]mIBG will be summarised (including those occurring post [^{123}I]mIBG administration).

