4.1 General Principles

All endpoints will be summarised using descriptive statistics. Rates will be summarised using counts and percentages, continuous variables will be summarised using n, mean, standard deviation, median and quartiles. Demographics will be presented for all patients in the safety analysis sets. Total numbers of patients in each analysis set will be given with explanations for any exclusions.

Agreement between the same endpoints measured using different modalities will be reported using descriptive statistics only (summary measures of agreement with 95% confidence intervals, and cross-tabulations or line listings directly comparing two sets of measurements) unless specified below.

Additional data may be summarised by CRUK as required for reporting and will be documented separately in the Clinical Study Report.

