4.2 Analysis Methods

4.2.1 Primary endpoint

SIOPEN total numbers of lesions detected on [¹²⁴I]mIBG vs [¹²³I]mIBG will be compared as follows:

In the first stage, a total of at least 9 evaluable patients will be recruited, with a combined total of at least 50 lesions positive on [¹²⁴I]mIBG PET/CT. Initially an exact one-sided binomial test of the null hypothesis: $p \geq 97\%$ will be done using $\alpha = 0.05$. If this is rejected in favour of the alternative hypothesis $p < 97\%$, the study will be stopped early for futility.

If the null hypothesis is accepted, a further one-sided binomial test of the null hypothesis, $p \leq 90\%$ will be done using $\alpha = 0.025$. If this is rejected in favour of the alternative hypothesis $p > 90\%$ then the study may be stopped early for efficacy. If this null hypothesis is not rejected, the study will continue to the second and final stage.

Only if following the interim analysis recruitment is to continue, a second stage will be required and will end when an overall total of at least 33 evaluable patients with at least 100 lesions have been recruited. An exact one-sided binomial test of the null hypothesis, $p \leq 90\%$, will be done using $\alpha = 0.025$. If this is rejected in favour of the alternative hypothesis $p > 90\%$ then the study will be declared a success.

All above tests will be done using the following method: For each patient, the total number of lesions assessed as positive by consensus opinion (with confidence score 4 or 5) on [¹²³I]mIBG planar scintigraphy is referred to as n_{123} , and the total number of lesions assessed as positive by consensus opinion (with confidence score 4 or 5) on [¹²⁴I]mIBG PET/CT is referred to as n_{124} , with the minimum of these two numbers known as n_{\min} . The primary endpoint will be reported by the sum of n_{\min} over all patients, divided by the sum of n_{123} over all patients.

In addition, for each patient the difference and ratios between n_{123} and n_{124} will be calculated and the distribution of these variables will be summarised using the median, upper and lower quartiles. The number and percentage of patients with n_{124}/n_{123} less than 1, equal to 1 and greater than 1 will be reported.

Population to be used: Evaluable population & sensitivity population

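### The stated alpha of 0.03 and power of 82% hold for independent lesions at 50 interim and 100 total lesions, and no patient-clustered bound is planned beside the pooled binomial result

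*Combined protocol and SAP*

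**What the plan says.** Protocol section 12.1 sets out a two-stage design on lesions, with a null agreement of 90% and an expected agreement of 97%. It declares that "Lesions are assumed to be independent within patients for the primary analysis" and concludes: "Overall this design has 82% power and an alpha of 0.03". SAP section 1.4 repeats the figures ("The overall study design including the second stage has 82 % power"), and SAP section 2.1 restates the assumption for the evaluable population: "All lesions from these patients are considered independent of one another".

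All three decisions (interim futility, early efficacy, final success) use an exact one-sided binomial test on pooled lesions (protocol 12.1 and 12.2.1; SAP 4.2.1 and 5). Cut-offs are given only for 50 and 100 lesions, but both counts are minimums, and protocol 12.2 adds: "Therefore, the total number of lesions is expected to be more than 50".

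Three elements bear on robustness:

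- SAP 4.1 plans "summary measures of agreement with 95% confidence intervals" and names no clustered method.
- SAP 4.2.1 runs the primary analysis in two sets ("Population to be used: Evaluable population & sensitivity population"). The second set is evaluable patients with fewer than 10 lesions.
- SAP 4.2.1 summarises per-patient differences and ratios of the two lesion counts.

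The visible text of the SAP addendum adds no clustered method.

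**The concern.** Lesions in one patient share one injection of each tracer, one PET/CT scan, one interval between scans and one consensus read. A poor scan or a real change between scans could affect several of them together, so positive correlation is a realistic possibility. The interim decision may rest on as few as 9 patients.

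Positive correlation makes the pooled count more variable than a binomial count. At the same lesion counts, the false-success rate then lies above its independent-lesion value, and the pooled exact lower bound is too high. The scans do not guide care, and success leads to larger studies (protocol 2.6). What is at stake is therefore how strong the evidence for that step appears to be.

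**Working it through.** **Inputs from protocol 12.1.** Null agreement 0.90; expected agreement 0.97; interim n = 50 from at least 9 patients; total N = 100 from at least 33 patients; futility test at level 0.05 against 97%; efficacy tests at level 0.025 against 90%; expected median 3 lesions per patient.

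**Inputs assumed.** The ICC (0 to 0.2) and how lesions are spread over patients.

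**Step 1: cut-offs at 50/100.**

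- Futility: P(X ≤ 45 | 50, 0.97) = 0.017 and P(X ≤ 46 | 50, 0.97) = 0.063, so stop at 45 or fewer.
- Early efficacy: 0.90^50 = 0.0052, while P(X ≥ 49 | 50, 0.90) = 0.0052 + 50 × 0.1 × 0.90^49 = 0.034, so 50/50 is needed.
- Final: P(X ≥ 96 | 100, 0.90) = 0.0237 and P(X ≥ 95 | 100, 0.90) = 0.058, so 96 is needed.

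**Step 2: reproduce the plan.** P(success) = P(X1 = 50) + Σ over x = 46 to 49 of P(X1 = x) × P(X2 ≥ 96 − x).

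| Quantity | Recomputed | Stated |
|---|---|---|
| Alpha (agreement 90%) | 0.0052 + 0.0214 = 0.0266 | 0.03 |
| Power (agreement 97%) | 0.2181 + 0.6034 = 0.8215 | 82% |
| Early efficacy at 97% | 0.97^50 = 0.218 | 22% |
| Futility at 90% | 0.569 | 57% |

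All four agree with the plan. The synopsis and protocol 3.3 instead put the futility limit at fewer than 45. This changes neither alpha nor power, because 45/50 cannot reach 96/100.

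**Step 3: add within-patient correlation.** Each patient's count is beta-binomial with mean P and correlation ICC. The patient distributions are convolved exactly and the cut-offs stay as in Step 1. The interim layouts are:

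- A: 17 patients of about 3 lesions (16×3 + 2), closest to the stated median.
- B: 9 near-equal patients (5×6 + 4×5).
- C: 9 skewed patients (1, 2, 2, 3, 3, 4, 5, 10, 20).

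The other 50 lesions are spread evenly over patients up to 33. Overall alpha at 90% agreement:

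| ICC | A | B | C |
|---|---|---|---|
| 0 | 0.027 | 0.027 | 0.027 |
| 0.05 | 0.033 | 0.036 | 0.045 |
| 0.1 | 0.040 | 0.047 | 0.064 |
| 0.2 | 0.055 | 0.072 | 0.103 |

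Power at 97% stays between 0.79 and 0.82 throughout. At ICC 0.1 the rise through the early stop and through the final test is 0.003 and 0.010 (A), 0.009 and 0.011 (B), 0.019 and 0.019 (C). Neither decision carries the whole effect.

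**Step 4: lower bounds.** The one-sided 97.5% bound is the P that solves P(X ≥ x | P, ICC) = 0.025. Ranges run over layouts A to C.

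| Result | ICC 0 | ICC 0.1 | ICC 0.2 |
|---|---|---|---|
| 50/50 | 92.9% | 90.1–92.2% | 87.9–91.4% |
| 96/100 | 90.1% | 88.8–89.5% | 87.8–88.9% |
| 97/100 | 91.5% | 90.3–90.9% | 89.4–90.4% |

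**Step 5: other lesion counts.** Cut-offs are re-derived at the stated test levels. With 50 interim lesions:

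| Total | Alpha, ICC 0 | Power, ICC 0 | Alpha, ICC 0.1, layout A |
|---|---|---|---|
| 100 | 0.027 | 0.82 | 0.040 |
| 105 | 0.020 | 0.80 | 0.032 |
| 110 | 0.016 | 0.77 | 0.026 |
| 113 | 0.013 | 0.757 | 0.023 |
| 114 | 0.027 | 0.872 | 0.043 |

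With the total fixed at 100 and 54 interim lesions, the level-based rule stops for efficacy at 53/54 and alpha is 0.039 at ICC 0. The synopsis and protocol 3.3 describe that stop as needing every lesion, which would be stricter.

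**Scope.** These figures model lesion-matched agreement, the protocol's endpoint. In SAP 4.2.1 ("The primary endpoint will be reported by the sum of" per-patient minimum counts), the numerator is never below the matched count. At the same true matched agreement, its false-success rate therefore cannot be lower.

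**The case against.** The case for leaving the plan alone has real strength.

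- **The assumption is disclosed.** Independence is stated next to the design, the exact binomial basis is named, and the text warns that interim lesions will exceed 50. This stands: a careful reader is told what the figures rest on, but not how far they move.
- **There are mitigations.** The under-10-lesion run would remove the two largest patients of layout C, the per-patient ratios would partly show where misses concentrate, and the early-efficacy stop is discretionary. These stand as partial help. The under-10 run still treats lesions as independent, and the ratios are descriptive.
- **The largest alphas come from strained layouts.** Layout B has a median of 6 lesions against an expected 3, and layout C puts 30 of 50 lesions in two patients. This stands too: layout A is closest to the stated median and gives 0.033–0.040 at ICC 0.05–0.1.
- **More lesions can help.** A reader might infer that any positive correlation takes the error rate above 0.03, or that exceeding the minimum counts inflates it. The documents support neither. The independent value is 0.0266, so a small ICC can stay below 0.03. At ICC 0.1, layout A gives 0.026 at 110 total lesions and 0.023 at 113. Under independence, the totals above 100 in Step 5 give 0.013–0.027.

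**Conclusion.** The point holds as a robustness gap. The stated alpha and power are correct for the case they describe, but the plan gives no values for correlated lesions or other counts, and the visible text plans no patient-clustered bound. Positive within-patient correlation raises the false-success rate above its independent-lesion value at the same counts, and the rate can exceed 0.03. At 50/100 lesions and ICC 0.1 it is 0.040–0.064, and the lower bound for 96/100 falls just under the 90% the trial aims to exceed. Power is little affected. Lesion count alone is a minor discreteness effect in both directions.

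All clustered figures depend on the assumed ICC and layouts. A reader might go further and infer that the design is miscalculated or that a success under it would be invalid. The documents do not support that: the arithmetic is right, the assumption is declared, and the true ICC is unknown. Redacted tertiary sections could not be checked, but the primary-endpoint sections are visible.

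**What to change.** Amend protocol 12.1 and 12.2.1 and SAP 1.4, 4.2.1 and 5.

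1. **Main change.** At the interim and final analyses, report beside the pooled proportion a one-sided 97.5% lower bound for lesion-matched agreement with the patient as the cluster, for example from a beta-binomial model. When agreement is 100% the ICC cannot be estimated, so show the bound over an ICC range. Consider it in the discretionary early-efficacy decision and in interpreting the final claim. Keep the planned binomial tests and boundaries. If the bound is added after the November 2020 statistical report review mentioned in the SAP addendum, label it as not pre-specified.
2. **Supporting change.** State that alpha 0.03 and power 82% assume independent lesions and 50/100 counts, and give both over an ICC range (for example 0 to 0.2) and at the actual interim and final counts.

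The cost is wording and one short exact calculation, with no extra patients or scans. The quoted alpha may look less favourable, and a borderline 96/100 would appear beside a clustered bound just under 90%. A binding clustered criterion is not proposed: at ICC 0.1 it would leave the 50/50 decision unchanged but move the final boundary to 97/100 and cut power to about 67–68%.
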